**A pilot study of cilostazol to improve quality-of-life and long term patency after open or endovascular
revascularization for peripheral artery disease**

October 24, 2018

NCT #02374957

A pilot study of cilostazol to improve quality-of-life and long term patency after open or endovascular revascularization for peripheral artery disease

Principle Investigator

[name]

Background

Cilostazol is considered a cAMP (phosphodiesterase) inhibitor and is the only medication approved for use in peripheral arterial disease (PAD) patients to reduce claudication symptoms. Contemporary data has demonstrated Cilostazol to improve patency after endovascular interventions in multiple randomized trials and retrospective studies in both critical ischemia and claudication patients.¹⁻⁵ Recent meta-analysis showed decreased restenosis, target vessel revascularization and major amputation in patients receiving Cilostazol.⁶ Cilostazol has also been shown to improve adverse outcomes after coronary stent implantations.⁷ Cilostazol was also shown to be equivalent to warfarin anticoagulation in a small, randomized trial for femoral-popliteal bypass for graft patency.⁸

Peripheral vascular graft or angioplasty/stent failure, especially early, is caused by intimal hyperplasia and smooth muscle activation and proliferation. No human studies have shown a role of Cilostazol in curtailing these, but animal research provides insight into potential therapeutic strategies to reduce early graft or angioplasty/stent failure. In one animal model, Cilostazol was associated with decreased intimal hyperplasia in a vein graft.⁹ Cilostazol reduces smooth muscle constriction and proliferation in animal models and also promotes angiogenesis in non-primate models.¹⁰⁻¹²

Cilostazol has been shown to be safe for long term use in patients with vascular disease.^{7,13} Cilostazol is contraindicated for use in patients with congestive heart failure due to decreased survival associated with use of other cAMP inhibitors in patients with Class III/IV CHF. No direct studies for Cilostazol have been undertaken in this regard. Cilostazol is also contraindicated in patients with allergic response to the drug, bleeding diathesis, intracranial bleeding or active bleeding peptic ulcer disease. It is not approved for use in pregnancy due to fetal defects and also shown to be excreted in milk.

Cilostazol use after peripheral revascularization has been sporadic and there has been no research to estimate patient quality of life with use of Cilostazol after open or endovascular lower

extremity revascularization. Moreover, prior randomized trials, as mentioned above, have all been performed in Japan, therefore results may not be generalizable to North American population.

Methods

We propose to study the effect of Cilostazol on patient quality of life (measured using standard QOL assessment tools in PAD patients (EQ-5D and EACH Qc) and relation of these to patency after lower extremity infra-inguinal bypass and endovascular interventions (angioplasty with or without stent placement) in a stratified randomized trial. Secondary endpoints would be limb salvage, minor (distal to calcaneus) and major amputation, claudication symptoms and distance and ischemic rest pain, stroke or other cardiovascular events, and overall survival. Adverse outcomes would also be collected, including - bleeding, need for blood transfusion, medication reaction (allergic or bleeding episodes), and cardiopulmonary failure.

This is a prospective investigator initiated single-center open-label, non-placebo controlled pilot study. All patients meeting the inclusion criteria would be screened for eligibility and after informed consent, randomization would be performed to either the Cilostazol treatment (drug group) or the non-Cilostazol treatment (control group) groups, stratified for endovascular or open interventions, using a closed envelope randomization technique. Eligible patients would be consented prior to surgery or within 48 hours of index procedure. Patients on Cilostazol prior to surgery would still be eligible and medication discontinued if randomized to control group. Cilostazol will be provided to patients randomized to the treatment arm free of charge for three months. . If you are randomized to the treatment arm (receiving Cilostazol) we will provide you with Cilostazol 100 mg, twice a day, free of charge for a period of three months. Patients who have renal impairment (problems with their kidneys) will be given 50 mg, twice a day instead of 100 mg, twice a day. Cilostazol has a half- life of 13 hours, therefore a washout period will not be necessary. Concurrent medication use based on comorbidities including diabetic, anti-hypertensive medications, lipid lowering agents would be prescribed based on standard practice and not dependent on study group or enrollment in the study. Also concurrent use of single or dual antiplatelet therapy (aspirin with or without ADP receptor blocker or similar medication) would be used at discretion of treating physician. Patients who need to be on anticoagulation, with warfarin or other oral anticoagulants, for high risk revascularization or other comorbidities, would have single antiplatelet agent (as above) only for secondary prevention of thrombotic events. Cilostazol use in either group would not lead to a change in their antiplatelet/anticoagulation regimen.

Pre-operative demographic, medication use and co-morbidity data and operative data would be retrieved from EMR. Patient follow up would be based on our current standard protocol which includes duplex of the graft or intervened artery at 4-6 weeks and 3-6 months. Cilostazol will be provided to patients free of charge for three months. Restenosis is defined as stenosis>50% based on our current vascular laboratory criteria or based on arteriogram imaging if performed at discretion of treating physician. Clinical examination and medication use and other secondary and adverse outcomes would be evaluated and QOL questionnaires administered at above time points. Quality-of-life (QOL) questionnaires (EQ-5D and EACH Qc) will be administered at enrollment and each follow up visit.

Purpose

The primary purpose of this pilot study is to collect QOL data on patients undergoing peripheral revascularization in order to determine the sample size required for adequate powered trial of Cilostazol versus usual care without Cilostazol and its effect on QOL. Thirty patients, fifteen in each arm, will be recruited into the pilot study in order to obtain sufficient data needed to estimate the variance and within-subject correlation of the outcome measures.

Benefits/Risks

Benefits include: possible improvement in quality of life for patients suffering from claudication after revascularization, improvement in graft patency and decreased restenosis and potential amputation. Risks include possible allergic reaction to the drug.

Inclusion

1. Patients should be older than 35 years of age
2. Patients treated for atherosclerotic PAD
3. Able to provide informed consent
4. Lower extremity open or endovascular revascularization, including bypass (autogenous or prosthetic), angioplasty and/or stenting, with or without concomitant aorto-iliac intervention.

Exclusion

1. Known congestive heart failure Class III/IV, systolic, acute or chronic
2. Allergic reaction to phosphodiesterase inhibitors
3. Intracranial bleeding within 3 months or active bleeding peptic ulcer disease
4. Traumatic vascular injuries requiring revascularization

5. Pregnant or breast feeding women, or plan to get pregnant over the study period (for five years after enrollment)
6. Planned ipsilateral major amputation within 30 days of index procedure
7. Moderate to severe hepatic impairment

Analysis

Data will be collected and stored on a password protected secure server which only study team members can access. QOL instruments (EQ-5D and EACH Qc) will be scored from the baseline, 4-6 week and 3 month visits. Cross-sectional and change scores will be calculated to estimate effect size and variance of QOL outcomes measures. These data will be used to assess potential efficacy and to project sample size requirements for a future trial. Treatment arm differences in early (4-6 week) and late (3 month) month changes in QOL scores will be tested using two-group t-tests.

Follow-up graft patency will be assessed as a secondary outcome and will be measured early (within 14 day of intervention) and late (six weeks and three months) using duplex ultrasound.

Treatment arm differences time to patency failure will be compared using Kaplan-Meier survival curves and log-rank tests. Information on the following tertiary outcomes will also be ascertained at six weeks and three months follow-up: (1) amputation, (2) death due to any cause, (3) clinical symptoms of claudication or rest pain (critical limb ischemia), and (4) stroke. Statistical comparison for differences between groups will not be performed for tertiary outcomes due to small sample size and power.

Confidentiality and Privacy

Confidentiality will be protected by collecting only information needed to assess study outcomes, minimizing to the fullest extent possible the collection of any information that could directly identify subjects, and maintaining all study information in a secure manner. To help ensure subject privacy and confidentiality, only a unique study identifier will appear on the data collection form. Any collected patient identifying information corresponding to the unique study identifier will be maintained on a separate master log. The master log will be kept secure, with access limited to designated study personnel. Following data collection subject identifying information will be destroyed at the earliest opportunity, consistent with data validation and study design, producing an anonymous analytical data set. Data access will be limited to study staff. Data and records will be kept locked and secured, with any computer data password protected. No reference to any individual participant will appear in reports, presentations, or publications that may arise from the study.

Data and Safety Monitoring

The principal investigator will be responsible for the overall monitoring of the data and safety of study participants. The principal investigator will be assisted by other members of the study staff.

Reporting of Unanticipated Problems, Adverse Events or Deviations

Any unanticipated problems, serious and unexpected adverse events, deviations or protocol changes will be reported to the principle investigator and the Institutional Review Board by the study coordinator within seven business days of the event.

Financial reimbursement

No reimbursement will be provided to the patients or investigators for this study. All follow up is consistent with our current protocol in the care of these patients. Cilostazol will be provided to those patients randomized to the treatment arm free of charge for three months. At the end of the three month period, providers may choose to prescribe Cilostazol for patients if they want to continue the drug.

Reference List

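### Bleeding diathesis is a stated contraindication to cilostazol but is missing from the seven exclusions, so an affected patient could be randomized to the drug

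*Combined protocol and SAP*

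**What the plan says.** The Background section gives the contraindications in one paragraph. After heart failure, it states: "Cilostazol is also contraindicated in patients with allergic response to the drug, bleeding diathesis, intracranial bleeding or active bleeding peptic ulcer disease". It then adds pregnancy and breast feeding as restrictions.

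The Exclusion section has seven numbered items. The only one about bleeding is Exclusion 3: "Intracranial bleeding within 3 months or active bleeding peptic ulcer disease".

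Methods sets the background antithrombotic therapy for both arms. For antiplatelet agents, "single or dual antiplatelet therapy (aspirin with or without ADP receptor blocker or similar medication) would be used at discretion of treating physician". For anticoagulated patients, it says that those taking "oral anticoagulants, for high risk revascularization or other comorbidities, would have single antiplatelet agent (as above) only for secondary prevention of thrombotic events". The protocol adds: "Cilostazol use in either group would not lead to a change in their antiplatelet/anticoagulation regimen".

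Bleeding also appears in three places outside eligibility, or might be expected there:

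- Methods lists the adverse outcomes to be collected: "bleeding, need for blood transfusion, medication reaction (allergic or bleeding episodes), and cardiopulmonary failure".
- Benefits/Risks says: "Risks include possible allergic reaction to the drug". Bleeding is not mentioned.
- Serious and unexpected adverse events "will be reported to the principle investigator and the Institutional Review Board by the study coordinator within seven business days of the event".

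**The concern.** The eligibility rules conflict with the protocol's own safety statement. The Background says the drug should not be given to someone with a bleeding diathesis, yet nothing in the criteria stops that person from being enrolled and assigned to it by envelope. Consent may be taken before surgery or up to 48 hours after the index procedure, so treatment may begin close to an invasive vascular intervention, and other antithrombotic drugs may be in use.

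What is at stake is the safety of any such participant. The pilot's estimates of variance and within-subject correlation, its t-tests and its log-rank comparison do not depend on this point.

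**Working it through.** No formula applies, and the plan gives no figure to reproduce. The check sets the Background restrictions against the eligibility criteria and then counts the agents that Methods allows.

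**Step 1. Each Background restriction against the exclusions**

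| Restriction in Background | Matching exclusion |
|---|---|
| Heart failure | No. 1, for Class III/IV |
| Allergy to the drug | No. 2, as allergy to the drug class |
| Bleeding diathesis | None |
| Intracranial bleeding | No. 3, within 3 months |
| Actively bleeding peptic ulcer | No. 3 |
| Pregnancy, breast feeding | No. 5 |

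The other exclusions concern traumatic vascular injury (no. 4), a planned major amputation (no. 6) and liver impairment (no. 7). Exclusions naming bleeding diathesis or a clotting disorder: 0 of 7. It is the only restriction in that paragraph with no counterpart.

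**Step 2. The inclusion criteria.** The four items cover age, atherosclerotic disease, capacity to consent and type of revascularization. None screens for a bleeding tendency.

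**Step 3. Whether Exclusion 3 covers it indirectly.** A diathesis is a standing tendency to bleed. A patient can have one without a recent intracranial bleed and without an actively bleeding ulcer. Such a patient passes Exclusion 3.

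**Step 4. Background agents allowed in Methods**

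- Antiplatelet route: aspirin + ADP receptor blocker = 1 + 1 = 2.
- Anticoagulant route: oral anticoagulant + one antiplatelet agent = 1 + 1 = 2.
- Ceiling without assigned cilostazol: max(2, 2) = 2.
- Ceiling in the drug arm: 2 + 1 = 3, because adding cilostazol does not change the background regimen.

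This ceiling applies to any drug-arm patient. It shows that the plan does not step down background therapy when cilostazol is added; it does not measure the eligibility gap, which exists whatever else the patient takes.

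**Step 5. Exposure.** Thirty patients are planned, fifteen per arm, so about 15 at most would be assigned cilostazol, supplied for three months. How many might have a diathesis cannot be derived, since no prevalence is given.

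**The case against.** The strongest reply is that the practical consequence is probably small. The trial is open-label and at a single center. The team wrote the contraindication into its own protocol, so it knows of it. Comorbidity data come from the medical record, where a known diathesis could be seen. Antiplatelet therapy is left to the treating physician, and a clinician may decline to enroll such a patient. Bleeding and transfusion are collected, the investigator monitors safety, and reporting is due within seven business days. All of this stands as mitigation. None of it is a written bar to enrollment, and the collection and reporting provisions act only once an event has occurred.

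A reader might infer several stronger points that the documents do not support:

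- *That affected patients would be on three antithrombotic agents.* Three is a ceiling. Reaching it requires a physician to choose or continue the fullest permitted background regimen for a patient with a known diathesis.
- *That the cited coronary-stent meta-analysis, whose title refers to triple antiplatelet therapy, shows the hazard.* That label does not fit an anticoagulant, one antiplatelet agent and cilostazol, which contains only two antiplatelet drugs. The Background cites the study for better outcomes and for safety, so it is not evidence of harm here.
- *That the 3-month limit on intracranial bleeding is a second shortfall.* The Background does not say whether it means current bleeding or any history. If it means current bleeding, the exclusion is the broader of the two.
- *That limiting the heart-failure exclusion to Class III/IV is the same kind of omission.* The Background's reason for that contraindication refers to those classes, which accounts for the wording.
- *That participants were not told of a bleeding risk.* The brief risk statement names only allergy, but the consent form is not among the documents, so nothing can be concluded about it.

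**Conclusion.** The point holds. The protocol names bleeding diathesis as a contraindication and leaves it out of the exclusions, and no other section closes the gap. Following the plan as written permits a patient with a known bleeding diathesis to be randomized to cilostazol, without any reduction of a background regimen of up to two agents.

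It should be corrected on participant-safety grounds alone. The magnitude is unknown: no event rate or prevalence is available, exposure is limited to about 15 drug-arm patients, and clinical judgment may prevent most or all such enrollments. The conclusion rests on reading the numbered list of seven exclusions as complete and on taking the Background's statement of the contraindication at face value. No reason for the omission is given, and since every other restriction in the paragraph is carried over at least in part, it looks like an oversight rather than a decision.

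**What to change.** Put the words 'Known bleeding diathesis' at the head of Exclusion 3, as the first of three alternatives, and leave the existing intracranial-bleeding and peptic-ulcer terms unchanged. Add one note stating that taking the antiplatelet or anticoagulant therapy permitted in Methods does not by itself count as a bleeding diathesis. Without the note, the new wording could be read as excluding many of the patients the trial is meant to enroll.

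The cost is a short amendment of three words and one note. There may be slightly fewer eligible patients; the documents give no basis for a number. The target of thirty, the endpoints and the analysis stay as they are.

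### Allocation is by closed envelope in an open-label, single-centre trial, and nothing requires baseline QOL to be recorded before the arm is revealed or the allocation to be kept from recruiting staff

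*Combined protocol and SAP*

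**What the plan says.** The Methods section calls the trial a "prospective investigator initiated single-center open-label, non-placebo controlled pilot study". Screening comes first and allocation follows: "after informed consent, randomization would be performed to either the Cilostazol treatment (drug group) or the non-Cilostazol treatment (control group) groups". There are two strata, one for each type of procedure, and the mechanism is described only as "using a closed envelope randomization technique". The documents do not say how the sequence is generated, whether it is blocked, where the envelopes are kept, or who holds and opens them.

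The follow-up paragraph of Methods says the two QOL instruments (EQ-5D and EACH Qc) "will be administered at enrollment and each follow up visit". That is the only administration before follow-up, so it must supply the baseline scored under Analysis. Its position relative to the opening of the envelope is not stated.

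Under Purpose, "Thirty patients, fifteen in each arm, will be recruited into the pilot study", chiefly to estimate variance and within-subject correlation. Under Analysis, cross-sectional and change scores also feed an effect-size estimate and the projected size of a future trial. Early and late changes are compared between arms by two-group t-tests, with no baseline adjustment mentioned.

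**The concern.** Enrolment is a sequence of steps: approach, consent, questionnaires, envelope. The protocol fixes only that eligibility and consent come before randomization. A patient could therefore be consented, learn the arm, and then complete the baseline questionnaires on the same visit without any departure from protocol. The treatment is open and the measure is self-reported, so hope or disappointment about the arm, or the manner of the staff member giving the form, could colour the score from which all later change is measured.

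The second route is selection. If the people who approach patients also keep the envelopes, concealment depends on how those envelopes are made and handled, and the protocol sets no rule for either. Staff may have preferences: the Background presents the drug favourably, and Methods says patients already taking it stop if they are allocated to control.

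The quantity most exposed is the arm difference in QOL change, and with it the effect size carried forward to the next trial.

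**Working it through.** The plan gives no figure on this point to reproduce. The check is to set the stated steps side by side and follow a baseline shift through the stated analysis.

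**Order of events**

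| Step | Stated position |
|---|---|
| Eligibility screening | Before randomization (Methods) |
| Consent | Before randomization (Methods) |
| Baseline QOL | At enrolment; before or after the envelope not stated (Methods, follow-up paragraph) |
| Custody of allocation | Not stated |

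**Effect on the change-score comparison.** Let B and F be mean baseline and follow-up scores, with D for drug and C for control. The tested quantity is

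Δ = (F_D − B_D) − (F_C − B_C).

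If knowing the arm moves reported baseline by s_D in the drug group and s_C in the control group, and follow-up scores are otherwise unaffected, then

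Δ observed = Δ − (s_D − s_C).

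The coefficient is exactly 1, so the whole shift enters the result. Its sign depends on how patients react, and the documents do not settle that.

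**Leverage of individual patients.** With 15 per arm (Purpose), if k patients in one arm each shift by δ, that arm's mean moves by kδ/15. The range is from δ/15 = 0.067δ for one patient (k = 1) to δ for all of them (k = 15). This describes sensitivity; it does not estimate k or δ.

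**Effect on the next trial's size.** For a comparison of two means, the required number per arm is proportional to 1/Δ² for a given SD. Planning on the observed difference multiplies the required number by [Δ/(Δ − (s_D − s_C))]². A shift that shrinks the difference makes the next trial too large, and one that inflates it makes the next trial too small.

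**Effect on variance and correlation.** A shift equal for every patient in an arm leaves the within-arm variance and within-subject correlation unchanged. If only a fraction p of an arm shifts by δ, unrelated to their true scores, baseline variance rises by p(1 − p)δ² while the covariance with follow-up is unchanged, so the correlation falls. The primary purpose is therefore less exposed than the effect size, but not immune.

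**Parts not affected.** Cross-sectional follow-up scores do not use baseline and escape the reporting route, although not the selection route. Baseline adjustment would not repair a reporting shift: it would replace the coefficient 1 by the regression slope on baseline.

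**The case against.** The strongest reply is that closed envelopes can conceal allocation well if they are opaque, sealed, sequentially numbered and independently held, and that silence on these details is not evidence of poor practice. Eligibility and consent already come first. Collecting QOL at enrolment does not place it after randomization, and many sites would give the form before opening the envelope. The trial is a pilot of thirty whose main product is a variance and a correlation. All of this is fair. It limits the point to a risk the plan leaves open, and it keeps the severity low. It does not remove the point, because the plan also estimates an effect size and tests arm differences on change scores.

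A reader might go further and infer that staff can guess the next arm. The planned 15 per arm invites this: simple randomization would give exactly 15:15 with probability C(30,15)/2³⁰ = 14.4%, so some restriction of the sequence seems likely. But "Thirty patients, fifteen in each arm" is an overall recruitment figure. No block size or stratum size is given, and restriction is not stated. Predictability would follow from a restricted sequence with visible past allocations, not from envelopes as such, so the documents do not support a guess rate or a finding that the arm is guessable.

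A reader might also bring in the consent window: "Eligible patients would be consented prior to surgery or within 48 hours of index procedure". Consent after the procedure lets staff know the procedural result before approaching a patient, and may make some baselines pre-operative and others post-operative. It does not reveal the arm. It is a separate matter.

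**Conclusion.** The point holds as a gap in protection. In this open-label trial the protocol permits baseline QOL to be answered after the arm is known and does not keep allocation away from those who recruit. Baseline-reporting bias and selective enrolment therefore cannot be excluded. An arm-related baseline shift would enter the planned change-score difference in full, and through it the effect size for the future trial.

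The size of the bias cannot be computed from the documents, because they give neither the chance nor the extent of any shift. The conclusion assumes that the enrolment questionnaire is the baseline, that the t-tests are unadjusted as written, and that site staff handle the envelopes, which is natural in a single-centre study but not stated. It does not assume that bias occurred, that the next arm is predictable, or that thirty is the wrong number. This is a low-severity improvement, worth making because a better method than the stated one costs very little.

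**What to change.** Amend Methods to replace the envelopes with a computer-generated list, stratified by endovascular or open intervention and held off the clinical team, either in the data-capture system or by the statistician. Release each arm only after consent, eligibility and both baseline questionnaires have been recorded, and keep the time of each step so that the order can be verified.

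The cost is a short protocol amendment, a one-off set-up of the list and a few minutes more per enrolment. The sample size and clinical care do not change.

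The change has limits. It closes the route through early knowledge of the baseline arm and the route through handling of envelopes. It does not hide past allocations in an open-label trial, and varying block sizes would not stop someone from betting on the arm that is behind, so they are not offered as a remedy for that. It leaves follow-up QOL reporting unblinded and does not address the 48-hour consent window.

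### Baseline QOL is not fixed relative to the procedure or to open-label randomization, and it then enters raw change scores and unadjusted t-tests; adjusting for baseline is the main gain, and timing is a minor matter

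*Combined protocol and SAP*

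**What the plan says.** All references are to the combined protocol and SAP.

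- **Methods, on consent:** "Eligible patients would be consented prior to surgery or within 48 hours of index procedure". Randomization follows consent. The trial is open-label, and allocation is stratified only by endovascular or open intervention.
- **Methods, on follow-up:** the two QOL questionnaires "will be administered at enrollment and each follow up visit". The only items described as pre-operative are non-QOL data: "Pre-operative demographic, medication use and co-morbidity data and operative data would be retrieved from EMR".
- **Purpose:** 30 patients, 15 per arm, are recruited to give "sufficient data needed to estimate the variance and within-subject correlation of the outcome measures".
- **Analysis:** scores come from one baseline and two follow-up visits. "Cross-sectional and change scores will be calculated to estimate effect size and variance of QOL outcomes measures". The arm comparison is specified as follows: "Treatment arm differences in early (4-6 week) and late (3 month) month changes in QOL scores will be tested using two-group t-tests".

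No section defines baseline relative to the procedure or places the questionnaire before randomization. None says that timing will be flagged or used in the analysis. The t-tests adjust for neither the baseline score nor the randomization stratum.

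**The concern.** A patient who answers a QOL questionnaire within two days of a bypass may be in a different state from one who has not yet been operated on. If both count as baseline without a label, part of the spread in change scores reflects when the form was filled in. That touches the pilot's stated product, the variance and within-subject correlation for sizing a later trial.

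Two further points concern the same baseline. In an open-label trial, a questionnaire answered after the envelope is opened can be coloured by the allocation, and that would carry into the change score differently by arm. And subtracting baseline is a less efficient use of it than adjusting for it, whether or not timing is mixed.

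**Working it through.** **What can be reproduced.** The 30 patients are stated without alpha, power, effect size, SD or precision target, so there is no figure to re-derive. The documents give neither the share of post-procedure baselines, nor the shift in score, nor the recall periods of the instruments. What follows is an illustration under stated assumptions.

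**Model.** Baseline and follow-up each have SD 1 within a timing group, with correlation ρ. A share f of baselines is post-procedure and shifted by a constant δ (in SDs).

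- Var(baseline) = 1 + f(1−f)δ²
- Var(change) = 1 + Var(baseline) − 2ρ
- observed correlation r = ρ / √Var(baseline)
- future n with baseline adjustment is proportional to 1 − r²

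Example: ρ = 0.5, f = 0.5, δ = 1.0. Var(baseline) = 1 + 0.25 = 1.25. Var(change) = 1 + 1.25 − 1 = 1.25, against 1.00 without mixing (+25%; SD +11.8%). r = 0.5/√1.25 = 0.447. Adjusted n rises by (1 − 0.20)/(1 − 0.25) − 1 = 6.7%.

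| ρ | f | δ | Change variance | Observed r | Adjusted n |
|---|---|---|---|---|---|
| 0.5 | 0.1 | 0.25 | +0.6% | 0.499 | +0.2% |
| 0.5 | 0.3 | 0.5 | +5.25% | 0.487 | +1.7% |
| 0.5 | 0.5 | 1.0 | +25% | 0.447 | +6.7% |
| 0.7 | 0.3 | 0.5 | +8.75% | 0.682 | +4.8% |
| 0.7 | 0.5 | 1.0 | +41.7% | 0.626 | +19.2% |

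**Against the pilot's own precision.** With complete data on 30 patients (28 df), the 95% interval for an SD is √(28/χ²), or 0.79 to 1.35 times the estimate. The worst row above multiplies the SD by √1.417 = 1.19, which is inside that range. Fisher's z with n = 30 gives 0.17 to 0.73 around a correlation of 0.5, and 0.45 to 0.85 around 0.7. All the observed correlations in the table lie inside.

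**Arm difference.** If the questionnaire precedes allocation, the post-procedure share is equal between arms in expectation and the shift cancels. With 15 per arm, the chance difference in share has SD √(2f(1−f)/15): 0.11 at f = 0.10, 0.16 at 0.25 and 0.18 at 0.50. This noise is already part of the change-score variance, and so of the t-test's standard error.

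**Gain from adjusting for baseline.** With equal SDs and no mixing, residual variance relative to change-score variance is (1−ρ²)/(2−2ρ) = (1+ρ)/2. That is 0.65, 0.75 and 0.85 at ρ = 0.3, 0.5 and 0.7.

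With mixing, the ratio is (1−r²)/Var(change) for baseline adjustment alone and (1−ρ²)/Var(change) when a timing term is added:

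| ρ = 0.5 | Baseline only | Baseline and timing |
|---|---|---|
| f = 0.3, δ = 0.5 | 0.724 | 0.713 |
| f = 0.5, δ = 1.0 | 0.640 | 0.600 |

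The timing term supplies (0.724 − 0.713)/(1 − 0.713) = 4% of the reduction in the first case and (0.640 − 0.600)/(1 − 0.600) = 10% in the second. At ρ = 0.3 it supplies 1% to 2%, and at ρ = 0.7 17% to 29%. Most of the gain is ordinary baseline adjustment.

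**The case against.** The case against is strong on timing. Harm requires that enrollment means consent, that the 48 hours run after the procedure, that a material share of patients enrols then, and that scores shift. The documents support the second as the natural reading but give no figure for the share, which could be zero, or for the shift, which a long recall period would shrink. Under the constant-shift model the error is conservative: the later trial would be too large. If that trial kept the same window and raw change scores, the pooled figures would be the right inputs. Follow-up SDs and the correlation between the two follow-up visits do not involve baseline at all. These points stand, and they keep the timing issue minor.

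A timing term in the main model is also fragile. It cannot be estimated if nobody enrols after the procedure, and at a 10% share it rests on three patients. That stands too, so it belongs only in a sensitivity analysis.

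A reader might infer that timing cannot be recovered, because the Confidentiality and Privacy section says "subject identifying information will be destroyed at the earliest opportunity, consistent with data validation and study design, producing an anonymous analytical data set". The documents do not support that. Consent dates and operative data from the EMR would probably give the timing, and the wording leaves room to keep a derived flag. Whether dates survive is not stated, so recording the flag at collection is simply safer.

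The objection does not reach two things. The plan leaves open whether the questionnaire precedes open-label allocation, and the t-tests set aside a baseline score already collected and a stratum already used in randomization.

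**Conclusion.** The gap is real: baseline QOL is anchored only to enrollment, and its order relative to the procedure and to randomization is left open. As a timing problem it is minor. Its size cannot be determined from the documents, and every illustrated effect lies within the sampling error of a 30-patient pilot. Those figures rest on equal SDs, a constant shift, and an assumed share and correlation.

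A reader might go further and conclude that the arm comparison is biased, or that the pilot will leave the later trial underpowered. Neither follows. The arm difference is unbiased in expectation if baseline precedes allocation, and under the constant-shift model the sizing error runs towards too many patients.

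The more useful conclusion concerns the analysis. With equal SDs, a baseline-adjusted model has residual variance of about 0.65 to 0.85 of the change-score variance at correlations 0.3 to 0.7, with or without a timing problem.

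**What to change.** 1. State that the baseline EQ-5D and EACH Qc are completed before randomization, and record for each patient whether this was pre- or post-procedure. The 48-hour consent window and all 30 patients are kept.
2. Replace the change-score t-tests in the Analysis section with a linear model of the follow-up score on arm, baseline score and procedure stratum.
3. Report the SD and the baseline/follow-up correlation overall. Only if enough patients have post-procedure baselines, also report them pooled within timing groups, or add a timing term, as a sensitivity analysis. State the assumption of equal variance and correlation across timing groups. It matters: if the correlation were 0.5 pre-procedure and 0.2 post-procedure, the pooled value would be 0.7 × 0.5 + 0.3 × 0.2 = 0.41 at a 30% share and would describe neither group.

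Cost: one recorded field, some protocol wording and slightly more analysis work. The model estimates four coefficients (intercept, arm, baseline, stratum), leaving 26 residual df instead of 28. The t critical value becomes 2.056 instead of 2.048, and the 95% SD interval 0.79 to 1.37 instead of 0.79 to 1.35 times the estimate.
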